5.4.2 The NCBRF-TIQ Subscales

5.4.2.1 NCBRF-TIQ: Positive Social Subscale

The changes from baseline in the positive social subscale ratings at each post-baseline visit and endpoint will be compared among treatment groups using Kruskal-Wallis test (for the overall comparisons) and Wilcoxon rank-sum test (for the pairwise comparisons of Treatment 1 vs. Treatment 2, Treatment 2 vs. Treatment 3, and Treatment 3 vs. Treatment 4) for the ITT population. The Hodges-Lehmann estimators and associated 95% confidence intervals will be calculated for the median differences between Treatment 1 and Treatment 2, Treatment 2 and Treatment 3, and Treatment 3 and Treatment 4. Table 5.4.2.1.1 provides exploratory analysis results for overall and pairwise comparisons for positive social subscale for the ITT population. Table 5.4.2.1.2 provides summary statistics for positive social subscale for the restricted ITT population.

Listing 5.4.2.1.1 provides positive social subscale data for the ITT population.

5.4.2.2 NCBRF-TIQ: Overly Sensitive Subscale

The changes from baseline in the overly sensitive subscale ratings at each post-baseline visit and endpoint will be compared among treatment groups using Kruskal-Wallis test (for the overall comparisons) and Wilcoxon rank-sum test (for the pairwise comparisons of Treatment 1 vs. Treatment 2, Treatment 2 vs. Treatment 3, and Treatment 3 vs. Treatment 4) for the ITT population. The Hodges-Lehmann estimators and associated 95% confidence intervals will be calculated for the median differences between Treatment 1 and Treatment 2, Treatment 2 and Treatment 3, and Treatment 3 and Treatment 4. Table 5.4.2.2.1 provides exploratory analysis results for overall and pairwise comparisons for overly sensitive subscale for the ITT population. Table 5.4.2.2.2 provides summary statistics for overly sensitive subscale for the restricted ITT population.

Listing 5.4.2.2.1 provides overly sensitive subscale data for the ITT population.

5.4.2.3 NCBRF-TIQ: Oppositional Behavior Subscale

The changes from baseline in the oppositional behavior subscale ratings at each post-baseline visit and endpoint will be compared among treatment groups using Kruskal-Wallis test (for the overall comparisons) and Wilcoxon rank-sum test (for the pairwise comparisons of Treatment 1 vs. Treatment 2, Treatment 2 vs. Treatment 3, and Treatment 3 vs. Treatment 4) for the ITT population. The Hodges-Lehmann estimators and associated 95% confidence intervals will be calculated for the median differences between Treatment 1 and Treatment 2, Treatment 2 and Treatment 3, and Treatment 3 and Treatment 4. Table 5.4.2.3.1 provides exploratory analysis results for overall and pairwise comparisons for oppositional behavior subscale for the ITT population. Table 5.4.2.3.2 provides summary statistics for oppositional behavior subscale for the restricted ITT population.

Listing 5.4.2.3.1 provides oppositional behavior subscale data for the ITT population.

5.4.2.4 NCBRF-TIQ: Hyperactivity Subscale

The changes from baseline in the hyperactivity subscale ratings at each post-baseline visit and endpoint will be compared among treatment groups using Kruskal-Wallis test (for the overall comparisons) and Wilcoxon rank-sum test (for the pairwise comparisons of Treatment 1 vs. Treatment 2, Treatment 2 vs. Treatment 3, and Treatment 3 vs. Treatment 4) for the ITT population. The Hodges-Lehmann estimators and associated 95% confidence intervals will be calculated for the median differences between Treatment 1 and Treatment 2, Treatment 2 and Treatment 3, and Treatment 3 and Treatment 4. Table 5.4.2.4.1 provides exploratory analysis results for overall and pairwise comparisons for hyperactivity subscale for the ITT population. Table 5.4.2.4.2 provides summary statistics for hyperactivity subscale for the restricted ITT population.

Listing 5.4.2.4.1 provides hyperactivity subscale data for the ITT population.

5.4.2.5 NCBRF-TIQ: Inattention Subscale

The changes from baseline in the inattention subscale ratings at each post-baseline visit and endpoint will be compared among treatment groups using Kruskal-Wallis test (for the overall comparisons) and Wilcoxon rank-sum test (for the pairwise comparisons of Treatment 1 vs. Treatment 2, Treatment 2 vs. Treatment 3, and Treatment 3 vs. Treatment 4) for the ITT population. The Hodges-Lehmann estimators and associated 95% confidence intervals will be calculated for the median differences between Treatment 1 and Treatment 2, Treatment 2 and Treatment 3, and Treatment 3 and Treatment 4. Table 5.4.2.5.1 provides exploratory analysis results for overall and pairwise comparisons for inattention subscale for the ITT population. Table 5.4.2.5.2 provides summary statistics for inattention subscale for the restricted ITT population.

Listing 5.4.2.5.1 provides inattention subscale data for the ITT population.

5.4.2.6 NCBRF-TIQ: Withdrawal/Dysphoria Subscale

The changes from baseline in the withdrawal/dysphoria subscale ratings at each post-baseline visit and endpoint will be compared among treatment groups using Kruskal-Wallis test (for the overall comparisons) and Wilcoxon rank-sum test (for the pairwise comparisons

of Treatment 1 vs. Treatment 2, Treatment 2 vs. Treatment 3, and Treatment 3 vs. Treatment 4) for the ITT population. The Hodges-Lehmann estimators and associated 95% confidence intervals will be calculated for the median differences between Treatment 1 and Treatment 2, Treatment 2 and Treatment 3, and Treatment 3 and Treatment 4. Table 5.4.2.6.1 provides exploratory analysis results for overall and pairwise comparisons for withdrawal/dysphoria subscale for the ITT population. Table 5.4.2.6.2 provides summary statistics for withdrawal/dysphoria subscale for the restricted ITT population.

Listing 5.4.2.6.1 provides withdrawal/dysphoria subscale data for the ITT population.

5.4.2.7 NCBRF-TIQ: Disruptive Behavior Disorder (DBD) Subscale

The changes from baseline in the DBD subscale ratings at each post-baseline visit and endpoint will be compared among treatment groups using Kruskal-Wallis test (for the overall comparisons) and Wilcoxon rank-sum test (for the pairwise comparisons of Treatment 1 vs. Treatment 2, Treatment 2 vs. Treatment 3, and Treatment 3 vs. Treatment 4) for the ITT population. The Hodges-Lehmann estimators and associated 95% confidence intervals will be calculated for the median differences between Treatment 1 and Treatment 2, Treatment 2 and Treatment 3, and Treatment 3 and Treatment 4. Table 5.4.2.7.1 provides exploratory analysis results for overall and pairwise comparisons for DBD subscale for the ITT population. Table 5.4.2.7.2 provides summary statistics for DBD subscale for the restricted ITT population.

Listing 5.4.2.7.1 provides DBD subscale data for the ITT population.

5.4.2.8 NCBRF-TIQ: ADHD-Total Score

The changes from baseline in the ADHD-Total Score at each post-baseline visit and endpoint will be compared among treatment groups using Kruskal-Wallis test (for the overall comparisons) and Wilcoxon rank-sum test (for the pairwise comparisons of Treatment 1 vs. Treatment 2, Treatment 2 vs. Treatment 3, and Treatment 3 vs. Treatment 4) for the ITT population. The Hodges-Lehmann estimators and associated 95% confidence intervals will be calculated for the median differences between Treatment 1 and Treatment 2, Treatment 2 and Treatment 3, and Treatment 3 and Treatment 4. Table 5.4.2.8.1 provides exploratory analysis results for overall and pairwise comparisons for ADHD-Total Score for the ITT population. Table 5.4.2.8.2 provides summary statistics for ADHD-Total Score for the restricted ITT population.

Listing 5.4.2.8.1 provides ADHD-Total Score data for the ITT population.

5.5 SENSITIVITY ANALYSIS

As a sensitivity analysis, the changes from baseline in the NCBRF-TIQ conduct problem subscale scores at each post-baseline visit and endpoint will be compared among treatment groups using analysis of covariance (ANCOVA) with treatment and weight group as the main factors and the baseline value as the covariate. Table 5.5.1 provides the sensitivity analysis results for NCBRF-TIQ conduct problem subscale for the ITT population.

6. SAFETY ANALYSES

The safety and tolerability endpoints will be summarized for the safety population according to the treatment actually received. Statistical testing will be performed for some of the safety endpoints, but the resulting p-values will be used for descriptive purposes only.

Safety will be assessed by the monitoring of AEs, vital signs, clinical laboratory tests, physical examinations, and electrocardiograms (ECG), as well as by the Simpson-Angus scale, the Barnes Akathisia scale, and the Abnormal Involuntary Movement Scale (AIMS).

6.1 ADVERSE EVENTS

AEs will be classified into standardized medical terminology from the verbatim description (Investigator term) using the Medical Dictionary for Regulatory Activities (MedDRA).

Although a MedDRA term for a subject may be reported more than once, that subject will be counted only once in the incidence count for that MedDRA term. AEs will be presented in the summary tables by preferred term nested within System Organ Class.

Verbatim description and all MedDRA level terms, including the lower level terms, for all AEs will be contained in the subject data listings (Listing 6.1.1).

6.1.1 Overall Study

Adverse events that occur or worsen after the first administration of study medication are considered treatment-emergent and will be summarized in tables. For missing information, the most conservative interpretation will be assumed.

AEs will be summarized for each treatment group by presenting the incidence of AEs based on the number and percentage of subjects with AEs.

Table 6.1.1.1 will provide overall incidence of AEs for the Safety population. Table 6.1.1.2 will provide an incidence summary of AEs by System Organ Class, and Preferred Term for the Safety population.

Table 6.1.1.3 will provide an incidence summary of AEs by System Organ Class, Preferred Term, and Relationship to Study Drug for the Safety population. If a subject had two or more adverse events in the same system organ class (or with the same preferred term) with different relationships to study drug, then the event with the closest relationship to study drug will be used for that subject.

Table 6.1.1.4 will provide an incidence summary of AEs by System Organ Class, Preferred Term, and Severity for the Safety population. If a subject had two or more adverse events in the same system organ class (or with the same preferred term) with different levels of severity, then the event with the worst severity will be used for that subject.

6.1.2 By Demographic/Baseline Variables

Tables similar to those for the Overall Study (6.1.1.1 - 6.1.1.4) will be presented for the demographic/baseline variables listed below:

Sex – Tables 6.1.2.1 - 6.1.2.4

Race – Tables 6.1.2.5 - 6.1.2.8

Ethnicity – Tables 6.1.2.9 - 6.1.2.12

Weight (<30kg and ≥ 30kg) – Tables 6.1.2.13 - 6.1.2.16.

6.1.3 Deaths, Serious AEs, and Other Significant AEs

Listings (and tabular summaries, if warranted) of deaths, SAEs, and other significant AEs, including AEs resulting in treatment discontinuation, study drug dose reduction, and study drug interruption will be provided (Listings 6.1.3.1 through 6.1.3.5).

6.2 CLINICAL LABORATORY VALUES

Table summaries and by-patient listings of the laboratory test results will be presented. Laboratory testing will be broken down by Hematology, Chemistry, and Urinalysis tests. Tables 6.2.1 through 6.2.4 will provide summaries for Hematology and Chemistry respectively and associated shift tables. Listings 6.2.1 through 6.2.4 will provide by-patient listing for hematology, chemistry, urinalysis, and urine pregnancy tests respectively.

6.3 VITAL SIGNS, HEIGHT, WEIGHT AND BMI

Summary table of vital signs (HR, blood pressure, temperature, respiratory rate) and height and weight will be presented by treatment and by visit. This summary table will also include change from baseline by treatment and visit. Descriptive summary statistics (mean, SD, median, and range) for vital sign data and height and weight will be evaluated by treatment group. Table 6.3.1 provides the summary table for vital signs, heights, weights and BMI.

Individual listings will also be provided for these parameters (Listing 6.3.1).

6.4 ECG RESULTS

Table 6.4.1 provides overall ECG findings (normal, abnormal not clinically significant, or abnormal clinically significant). Table 6.4.2 summarizes ECG results (both actual values and change from baseline values) by visit by treatment group using descriptive statistics for quantitative ECG parameters: PR Interval (msec), QRS Duration (msec), QT Interval (msec), and QTcF Interval (msec). Table 6.4.3 presents the ECG Shift Table from Baseline to Post-Baseline Visits for qualitative ECG parameters.

Table 6.4.4 provides the number and percentage of subjects with any QTcF value ≥ 450 msec for all assessments made during the study as well as by scheduled collection and treatment group. This table also provides the number and percentage of subjects with any change from baseline in the QTcF of $\geq 30 - 59$ msec as well as ≥ 60 msec over all assessments made during the study as well as by visit and treatment group.

Listing 6.4.1 provides ECG Findings.

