3. DESIGN OF THE STUDY

3.1 STUDY DESIGN

This will be a randomized, multicenter, parallel group, dose-ranging safety and tolerability study in children with ADHD and persistent serious conduct problems. The target subjects are healthy male or female children aged 6 to 12 years, inclusive, with a diagnosis of ADHD with persistent serious conduct problems. To determine eligibility for the study, subjects will undergo an initial screening visit. Seventy-two subjects will be randomized in the study; assuming a 17% dropout rate, it is anticipated that 60 subjects will complete the study.

[figure not shown]
The study will consist of a Screening Period (within 28 days prior to the first dose administration), a Titration Period of 2 to 5 weeks, a Maintenance Period of 6 weeks, and a Safety Follow-up, which will be performed 30 days after the final study visit. The total subject duration in the study will be 16 to 19 weeks depending on the treatment group assignment. The total study duration is anticipated to be 15.5 months.

A total of 72 subjects will be randomized based on weight at baseline, to 1 of 4 treatment groups. A dose titration schedule will be followed (Table 1), where dosing for subjects < 30kg will be initiated at 1.67mg/day and dosing for subjects \geq 30kg or more will be initiated at 3.34mg/day. The titration schedule will be followed until the target dose (Treatment 1, 2, 3, or 4) is reached. Subjects will remain at the target dose for 6 weeks.

Table 1. Dose Titration Schedules (mg/day)

Week	1	2	3	4	5	6
Treatment Weight	Titration	Titration	Titration or Treatment 1	Titration or Treatment 2	Titration or Treatment 3	Treatment 4
< 30kg	1.67 (1.67mg qhs)	3.34 (1.67mg bid)	5 (1.67mg tid)	10 (3.33mg tid)	15 (5mg tid)	20 (6.67mg tid)
≥ 30kg	3.34 (1.67mg bid)	5 (1.67mg tid)	10 (3.33mg tid)	20 (6.67mg tid)	30 (10mg tid)	40 (13.33mg tid)

A study schematic is presented below.

Following 2 weeks of titration, subjects randomized to Treatment 1 in each weight group will receive Maintenance Treatment 1 (5mg/day for children < 30kg and 10mg/day for children ≥ 30kg), while the remaining subjects will receive the same level of drug as a titration step to the next level (Maintenance Treatment 2: 10mg/day and 20mg/day) and so on until the final subjects in each weight group reach the highest doses (20mg/day and 40mg/day).

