3.6.5 Electrocardiograms (ECGs)

ECGs (12-lead) will be obtained at the Screening visit and the Final Visit as designated on the Schedule of Visits and Procedures. Additional ECGs may be performed at other times if deemed necessary.

The ECG will be recorded while the subject is resting in a supine position. The ECG will electronically measure the PR, QRS, QT, and QTc intervals, and heart rate.

All ECG tracings will be reviewed within 24 hours by the Investigator or sub-Investigator. PR intervals will be determined for each of these ECGs from a single reading. Invalid

measurements will be repeated. QTc will be reported as QTcF (QT corrected using Fridericia's method).

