5. EFFICACY ANALYSES

5.1 GENERAL CONSIDERATIONS AND STATISTICAL/ANALYTICAL ISSUES

5.1.1 Definition of Baseline

Unless stated otherwise, the first Titration Period visit will be considered as Baseline for statistical analyses. For calculation of changes from baseline, the last available measurement/assessment before the first study drug application will be used as Baseline measure.

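### The overall QTcF ≥ 450 msec row of Table 6.4.4 takes in the pre-drug Screening ECG, and the SAP describes no count of new-onset values

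*SAP*

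**What the plan says.** Section 6.4 assigns to Table 6.4.4 the "number and percentage of subjects with any QTcF value ≥ 450 msec for all assessments made during the study", and adds that the count is given "as well as by scheduled collection and treatment group". The next sentence adds changes from baseline in QTcF of 30 to 59 msec and of 60 msec or more, again over all study assessments and by visit and arm.

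On timing, section 3.6.5 states: "ECGs (12-lead) will be obtained at the Screening visit and the Final Visit as designated on the Schedule of Visits and Procedures". It allows further ECGs if needed. The schedule in section 3.4 shows the same two time points. Section 3.1 names the Screening Period as part of the study and places it within the 28 days before the first dose.

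On baseline, section 5.1.1 provides that "the last available measurement/assessment before the first study drug application will be used as Baseline measure". No ECG is scheduled at the first Titration visit, so the Screening ECG normally serves as the ECG baseline.

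On grouping, section 6 says safety endpoints are "summarized for the safety population according to the treatment actually received".

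**The concern.** An outlier count shown by dose arm is normally read as something seen on drug. On the plain wording, this row mixes values recorded on drug with values recorded before it. Tabulating a Screening value by treatment received is also awkward, since no treatment had been received.

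Other parts of the SAP draw the line that this row lacks. Section 6.1.1 limits the adverse event tables to events that begin or worsen after the first dose. Within section 6.4 itself, "Table 6.4.3 presents the ECG Shift Table from Baseline to Post-Baseline Visits for qualitative ECG parameters". Neither limit extends to the QTcF threshold count.

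Safety and tolerability of four doses is the primary objective (section 2.1), and every arm receives SPN-810, so safety is read by comparing doses. In small arms, one or two pre-drug values can create or mask an apparent dose pattern in this row.

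**Working it through.** The SAP states no result for this row, so there is no figure to reproduce. The check is of scope first, then of scale.

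**Inputs**
- Scheduled ECGs per child: 2, one before the first dose (sections 3.4 and 3.6.5).
- Randomized: 72 (section 3.2), allocated 1:1:1:1 within weight group (section 3.3), so about 72/4 = 18 per arm.
- p = probability that the Screening QTcF is ≥ 450 msec; q = the same for the Final Visit. The SAP gives neither. The values below are assumptions.

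**Scope.** Screening belongs to the study and the row covers all study assessments, so one of the two scheduled ECGs feeding it is pre-drug. A child with 452 msec at Screening and 430 msec at the Final Visit counts once in the overall row, once under Screening and not at all under Final Visit.

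**Weight of one child.** 1/18 = 5.6 percentage points of an arm.

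**Chance that an arm is affected.** For an arm of 18, the probability of at least one Screening value ≥ 450 msec is 1 − (1 − p)^18. The expected number among all 72 is 72p.

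| Assumed p | At least one in an arm of 18 | Expected in 72 |
|---|---|---|
| 1% | 17% | 0.7 |
| 2% | 30% | 1.4 |
| 5% | 60% | 3.6 |

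**Overall row against the post-dose rate q**, scheduled ECGs only:
- If the two ECGs are independent, the overall row is 1 − (1 − p)(1 − q).
- With p = q = 2%: 1 − 0.98² = 4.0%, against 2.0% post-dose.
- With p = q = 5%: 1 − 0.95² = 9.8%, against 5.0% post-dose.
- If p = q and the same children exceed 450 msec both times, the overall row equals q and there is no inflation.
- With p = 5% and q = 0%: 5.0% against 0%. The excess then consists wholly of pre-drug values.
- Under any dependence, the excess over q lies between 0 and p.

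**What is not affected.** The 30 to 59 msec and ≥ 60 msec categories measure change from baseline. The baseline ECG has zero change from itself, so it cannot enter them.

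**What is not provided.** The shift table in section 6.4 covers qualitative ECG parameters. The Screening and Final Visit rows of Table 6.4.4 are separate marginal counts. Neither identifies children who were below 450 msec at baseline and at or above it afterwards.

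**Unscheduled ECGs.** Section 3.6.5 allows extra ECGs and section 6.4 counts all assessments, but section 4 says unscheduled data are listed and left out of summaries. The two rules give different counts whenever an extra ECG is the only one at or above 450 msec.

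**The case against.** The strongest reply is that the needed figure is already in the table. Reporting by scheduled collection gives separate Screening and Final Visit counts for each arm, and the Final Visit assessments are also planned before early discontinuation. If unscheduled data stay out of summaries, a post-dose row would simply repeat the Final Visit row. This stands, and it is the main reason the point is minor. It does not correct the overall row, and it does not supply a new-onset count.

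The wording may also be loose rather than intended. The following sentence applies the same scope to change from baseline, where only post-baseline values can contribute, and the table shells are separate documents that may restrict the row. That is possible, but the SAP text does not say so.

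The row is also accurate as a count over the whole study. The SAP does not call it treatment-emergent, safety p-values are descriptive only (section 6), and no decision rule depends on it. That stands too. The remaining risk is misreading.

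A reader might infer that the reported outlier rate will be about double the on-treatment rate. The documents do not support this. Doubling needs independent ECGs with equal probabilities, whereas two readings from one child may well agree. Any Screening ECG limit among the protocol's eligibility criteria, which are not at hand, could bring p close to zero. Nor does the row favour any dose systematically: Screening values precede drug, so under randomization they differ between arms only by chance.

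**Conclusion.** The point holds for one row of one table. As worded, the overall ≥ 450 msec count includes pre-drug values, and a Screening-only value is charged to a dose arm at 5.6 percentage points per child, assuming 18 per arm. With equal Screening and Final Visit rates, the inflation runs from none to about double. Its actual size cannot be determined from the SAP, because neither rate is given. The rest of Table 6.4.4 is sound, and the on-treatment rate at the Final Visit is not hidden. What is missing is a count of children who newly reach 450 msec after dosing. Severity is minor: the output is descriptive, but the correction changes a reported safety figure and is nearly free.

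**What to change.** In section 6.4, and in a footnote to Table 6.4.4:
- Restrict the overall ≥ 450 msec row to ECGs recorded after the first dose.
- Split that row by baseline QTcF: new (baseline < 450 msec) and already ≥ 450 msec at baseline.
- Keep the Screening count as a separate, labelled baseline row.
- State whether unscheduled post-dose ECGs count. If they do, make this an explicit exception to the rule on unscheduled data in section 4. If they do not, replace the reference to all assessments with scheduled post-dose assessments.

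The cost is a few lines of SAP text, a footnote and a small change to the table program. No new data or visits are needed.
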